2.3 Study Design

V. Study Design and Methodology **Study Type and Sample Size**

This will be a pilot study performed at an urban academic center in south-side Chicago to collect preliminary data in hopes of conducting a larger, randomized intervention. Based on the last two years in our Thoracic oncology clinic at the University of Chicago, we estimate that 600 new patients will be seen over the 2-year period of this study, an amount that will easily provide the number of patients necessary to fulfill the requirement of this pilot study.

For this study, over 2 years, we will contact 150 new lung cancer patients of which 80% (120) will agree to participate in our study. Based on the current clinical trial portfolio in the Thoracic oncology clinic (**see Appendix 5**), which has grown substantially since our last study, it is estimated that trials are now technically available for about 80% of the new patient population (for our pilot of 120 patients that leaves about 100). Of our 100, we estimate, based on our previous work, that a clinical trial will actually be offered to 40% of these patients (40).

Patient Population/Recruitment

All new cancer patients presenting to the University of Chicago outpatient oncology clinics are currently pre-screened for cancer type and set up for appointments by our new patient intake coordinators. New patients with Non-Small Cell Lung cancer and Small Cell carcinoma will be contacted by our study coordinator who will call them 2-3 days prior to their appointment to ascertain their interest in participating in the research study. Those interested will be asked to arrive at their new visit 60-90 minutes prior to the appointment time.

Study Procedure

[figure not shown]
Patients will use the Talking Touchscreen (TT) to complete a pre-intervention survey which will ascertain clinical trial knowledge (detailed in SA#1, surveys in **Appendix 4**) and the following information using the instruments detailed in SA#4: socio-demographics, health literacy, anxiety, depression, and social support. They will then use the TT to view the NCI's educational module on "Taking Part in Cancer Treatment Research Studies". (see **Appendix 3** for a sample screen shot). The NCI

booklet will be adapted as an interactive multimedia learning program. This interactive program and the pre/post survey assessments will run on the same tablet PCs. The “Listen and Learn Modules” allow persons with diverse literacy and computer skills to learn and go at their own pace. Once the session is complete, patients will complete a post-intervention survey to measure any change in clinical trial knowledge and a feasibility (evaluation) survey (detailed in SA#2, survey in **Appendix 4**) to discern patient attitudes toward their using technology as a means of information collection and dissemination during their doctor’s visit. The researcher will also complete a simple questionnaire addressing the effect, if any, of introducing technology into the patient visit.

Talking Touchscreen Design and Implementation

The integration and programming of the measurement tools and the NCI’s “Taking Part in Cancer Treatment Research Studies” pamphlet (**Appendix 1**) into the TT will be handled by the Informatics team at Northwestern University’s Assessment Center (Assessment CenterSM; <http://www.assessmentcenter.net/>) and educational software developers at the CancerHelp Institute(www.cancerhelp.org) under the supervision of Co-PI [name], a medical sociologist and biostatistician, and a team including a Senior Developer, an IT Project Manger, and a user support specialist who will be available for logistic troubleshooting relating to hardware and software malfunctions which may occur. As detailed in the preliminary study section above, this group has significant expertise in the scope of work being performed in this study and in particular adapting interactive health messaging to low literacy health populations. Audio recordings for the TT will be done by Wordly Voices (<http://www.worldlyvoices.com/>) a company whose sole focus is on recording custom voice prompts.

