- High vs. Low HL: 77% vs. 48% ($p<0.0001$)
- White vs. AA: 83% vs. 56% ($p<0.0001$)

Clinical Trial Participation

As shown in **Table 1** below, overall 10% of our patients signed consent for a therapeutic clinical trial with African American patients more likely to sign consent. When a trial is available and offered, 41% of all patients and 63% of our African American patients sign consent. Those with higher health literacy are more likely to sign consent and to sign when offered.

Table 1: Clinical Trial Participation

	All	W	AA	p-value	HHL	LHL	p-value
Signed Consent	10%	10%	18%	0.07	12%	7%	0.2
Clinical Trial Available	57%	61%	46%	0.06	58%	54%	0.69
Offered if Available	35%	36%	31%	0.7	37%	30%	0.47
Signed if Offered	41%	37%	63%	0.2	42%	33%	0.6

W-White; AA-African American; HHH-High Health Literacy; LHL-Low Health Literacy

To better understand the findings regarding African American race and health literacy, we ran a multivariable logistic regression model that controlled for both variables. As displayed in **Table 2**, when controlling for health literacy, AA are 2 times more likely than whites to enroll in a clinical trial. Similarly, those with high health literacy are 2.5 times as likely to enroll as those with low health literacy, controlling for race.

Table 2-Signed Consent: Logistic Regression Models

	OR (bivariate)	95% CI	OR (multivariable)	95% CI
AA:White	1.9	0.9-3.7	2.1	0.8-5.2
HHL:LHL	1.8	0.6-4.9	2.5	0.8-7.8

These data are consistent with our hypothesis that low health literacy is a potential barrier to trial participation. These results also suggest that the impact may be particularly helpful for our African American patients since low health literacy is an intervenable factor which may be dampening what appears to otherwise be enthusiastic support for trial participation in our patient population.

Barriers to Participation

The number one reason that patients did not consent to a trial if offered was that they felt *overwhelmed by the information* (56%). Measured barriers which correlated with not signing consent if offered were lack of social support ($p=0.05$), lack of emotional support ($p=0.01$), high levels of anxiety (OR 0.51; 95% CI 0.13-1.87) and high levels of depression (OR 0.45;95% CI 0.09-2.08). Despite our *a priori* hypothesis that physician trust would play an important role, no measure of physician/institution trust predicted clinical trial enrollment at the University of Chicago.

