Hypothesis 2a: By providing the patient important information as to the options they may have in terms of their cancer treatment, directly prior to their talking with their physician and through use of an easy interactive tool, such as the proven TT in low-literacy populations, we will not interrupt or decrease the patient experience but enhance the physician-patient interaction, leading to increased participation in clinical trials.

This pilot study will provide to us the opportunity to understand the feasibility of using technology as a way to educate a cancer population about clinical trials within the healthcare environment of a busy, urban hospital setting. We will use this as an opportunity to understand how to integrate technology into clinic flow so that it is not disruptive but rather increases the efficacy of the physician-patient visit by educating patients as to clinical trials before seeing the physician. We estimate that the survey items will take 20-30 minutes to complete and that patients will spend **15-30 minutes with the TT**. Our experience is that 60 minutes is not an unreasonable burden, given the waiting time and other factors associated with a new visit. We will administer a simple evaluation questionnaire following the completion of the patient encounter with the TT, to measure their experience, including degree of difficulty.

Hypothesis 2b: The use of the TT will not effect clinic flow nor pose an additional burden to patient, physician or staff.

The researcher will also complete a simple questionnaire addressing the effect, if any, of introducing technology into the patient visit.

Data Analysis

We will administer a simple evaluation questionnaire to understand the patient's experience with the TT. We will adapt other questionnaires used in a previous TT study and will calculate descriptive summaries of the responses.

Specific Aim 3: *To evaluate the proportion of patients who sign consent to enroll in a cancer-specific treatment clinical trial when one is offered, compared to historical data.*

At the completion of the physician visit for that day, physicians will fill out a previously validated form asking the following questions:

- Is there a clinical trial here for this cancer and stage, regardless of the patient's other characteristics?
- Did you discuss a clinical trial with this patient?
- Did the patient specifically ask you about a clinical trial before you brought it up?

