	
Three subscales on the pre- and post-questionnaire will assess attitudes towards clinical trials, knowledge about clinical trials and perceived ability. Change scores will be calculated and evaluated using a paired t-test. A sample size of 120 will have 80% power to detect an effect size as small as 0.258 using a paired t-test with a 0.050 two-sided significance level.
 
Based on our previous study, we estimate that 60% of these patients will have high health literacy (72) and the remaining 40% (48) will have low health literacy. We will evaluate differences in pre- and post-test changes by health literacy group. We will also estimate the correlation between change scores and the continuous measure of health literacy.
 
For Specific Aims 3 and 4: Based on the current clinical trial portfolio in the Thoracic oncology clinic (see Appendix 4), it is estimated that trials are available for 80% of the new patient population (including patient eligibility) (100 patients over 2 years) and of these, 40% will be offered participation (40). Our previous data suggested that when offered, 40% of these patients will sign consent. We hypothesize that our TT intervention will increase both the percentage of patients offered a trial (because of active participation from the patient in inquiring about trials) and in the percentage of patients who sign when offered. These impacts will be most profound in the low literacy group.
 
An effect size of 0.20 (H0: 0.4, HA:0.6) is a reasonable estimate for this pilot to be able to produce a clinically significant improvement in cancer clinical trial enrollment. A sample size of 40 (those offered enrollment) should give us 80% power to detect a 20% difference in trial enrollment from our baseline hypothesized value of 40% at a one-sided alpha level of 0.05.

2.8 Specific Drug Supply Requirements
	
NA

2.9 Adverse Experience Reporting
	
NA

2.10 Itemized Study Budget
	
A preliminary study budget must be provided with the initial proposal submitted to give guidance to the MISP Review Committee as to the expected study costs. A refined itemized budget detailing the costs associated with the study should be provided with the final protocol or included in the study agreement as Exhibit B.

References

1. Comis RL, [name] JD, Aldige CR, et al: Public attitudes toward participation in cancer clinical trials. *J Clin Oncol* 21:830-5, 2003

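### The 40% offer rate behind Aim 3's sample size is credited to previous work that reports 35%; the documented inputs give about 34 offers, not 40, and power of roughly 70–77%

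*Combined protocol and SAP*

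**What the plan says.** Section 2.3 builds the Aim 3 denominator in three steps. Of 150 patients contacted, 80% (120) take part. Then "it is estimated that trials are now technically available for about 80% of the new patient population", and "for our pilot of 120 patients that leaves about 100". Finally, "Of our 100, we estimate, based on our previous work, that a clinical trial will actually be offered to 40% of these patients (40").

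Section 2.7 repeats the chain for Aims 3 and 4, with availability described differently: "it is estimated that trials are available for 80% of the new patient population (including patient eligibility) (100 patients over 2 years"). It then states the design: "A sample size of 40 (those offered enrollment) should give us 80% power to detect a 20% difference in trial enrollment", for 40% versus 60% at a one-sided alpha of 0.05. The test is not named.

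The previous work is summarised in Table 1 (Preliminary Studies, part A). Its columns are All, White, African American, p-value, high health literacy, low health literacy, p-value. The offer row reads "Offered if Available 35% 36% 31% 0.7 37% 30% 0.47", and the overall consent row reads "Signed Consent 10% 10% 18% 0.07 12% 7% 0.2".

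**The concern.** The number of patients offered a trial is the denominator of the Aim 3 comparison with historical data and the only basis for its stated power. The offer rate is attributed to earlier work, yet the row of Table 1 that measures it never exceeds 37% in any column. The entry in the All column that is close to 40% is *Signed if Offered* (41%), a different quantity. The step before also moves upward, from 96 to 100.

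A reader who checks the source cannot tell whether 40% is a rounded 35%, a rate on another denominator, or a figure that already allows for the rise in offers that section 2.7 hopes the tool will produce. The definition of availability adds to the doubt. Section 2.3 means technical availability, whereas section 2.7 says patient eligibility is included. The Aim 3 physician form asks "Is there a clinical trial here for this cancer and stage, regardless of the" patient's other characteristics, which matches 2.3 and not 2.7. An offer rate has no clear meaning until its denominator is fixed.

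At stake is a modest loss of power in a pilot. Because the pilot is meant to inform a larger randomised study, a misattributed planning rate could also be carried forward.

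**Working it through.** **Inputs.** 120 participants, 80% availability and 40% offered (2.3). 35% offered if available (Table 1, All). p0 = 0.40, p1 = 0.60, one-sided alpha 0.05, n = 40, power 80% (2.7).

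**1. The plan's own figure.** One-sample test against a fixed 0.40.
- Exact binomial: take the smallest r with P(X ≥ r | n, 0.40) ≤ 0.05; power is P(X ≥ r | n, 0.60). At n = 40, r = 22, attained alpha 0.0392, power 79.1%.
- Normal: power = Φ[(0.20√n − 1.645√0.24)/√0.24]. At n = 40 this is Φ[(1.265 − 0.806)/0.490] = 82.6%.

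The stated 80% is therefore right if 40 patients are offered a trial.

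**2. Offers from the documented inputs.**
- 120 × 0.80 = 96.
- 96 × 0.35 = 33.6, about 34.
- Rounding alone: 96 × 0.40 = 38.4. Offer rate alone: 100 × 0.35 = 35.
- Using the plan's 72 high / 48 low literacy split with Table 1's literacy-specific rates: 72 × 0.8 × 0.37 + 48 × 0.8 × 0.30 = 32.8, about 33.

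**3. Power at fixed n.**

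| n | exact r | exact alpha | exact power | normal power |
|---|---|---|---|---|
| 33 | 19 | 0.031 | 68.1% | 75.8% |
| 34 | 19 | 0.044 | 74.9% | 76.9% |
| 35 | 20 | 0.030 | 70.0% | 78.0% |
| 38 | 21 | 0.041 | 77.8% | 80.8% |
| 40 | 22 | 0.039 | 79.1% | 82.6% |

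From n = 40 to n = 34 the loss is 4.2 points (exact) or 5.7 (normal). Of the normal loss, 1.7 points come from rounding 96 to 100 (n = 40 to 38) and 3.9 from the offer rate (n = 38 to 34). Exact power is saw-toothed and n = 34 is a local peak, so 75% should not be read as a floor.

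**4. Random number of offers.** Averaging over Binomial(96, rate), power falls from 75.6% (rate 40%) to 70.7% (rate 35%) by the exact test, and from 80.8% to 76.0% by the normal approximation.

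**5. Detectable rate.** With n = 34 and 80% power, the detectable rate is 61.4% (exact) or 60.9% (normal), against the planned 60%.

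**6. How firm is 35%?**
- Multiplying Table 1's All column gives 0.57 × 0.35 × 0.41 = 8.2%, but signed consent is 10%. Solving for the offer rate, 0.10/(0.57 × 0.41) = 42.8% (39.8–45.9% allowing for rounding of the entries). That is 0.428 × 96 = 41 offers and normal power of 83.4%.
- The other columns back-solve to 44% (White), 62% (African American), 49% (high literacy) and 39% (low literacy).
- The documents do not give the number of earlier patients with a trial available. Assuming 57% of 338 or of 375 (193 to 214), the 95% interval for 35% is about 29–42%, which includes 40%.

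**The case against.** The strongest reply is that the plan rounds its inputs to the nearest ten throughout: 63%/37% literacy becomes 60%/40%, 41% signed if offered becomes 40%, and 96 becomes about 100. On that pattern 35% rounds to 40%, and the text claims only an estimate based on earlier work. This is probably the explanation, and the write-up should not imply anything worse. But it is not stated, and in these two steps the rounding goes the same way, turning about 34 into 40.

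It can also be said that Table 1 pools the cancer clinics while the plan concerns the thoracic clinic, and that Table 1 back-solves to 39% or more in every column. Both points stand. They make 40% plausible, but they do not make it the figure the source reports.

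Three other defences do not carry. The larger trial portfolio is already used to raise availability from 57% to 80%. The hoped-for rise in offers due to the tool is given no size and is not presented as part of the 40%. The added gastric clinic does not enter the sample-size text, which still counts 150 lung cancer patients.

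A reader might also infer a further error in Aim 3, which gives 30% enrolling when offered in the low-literacy group where Table 1 has 33%. The documents do not support treating that as a fault. It fits the same rounding as 41% to 40% in the sentence before it, and no test or power depends on it.

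**Conclusion.** The point holds in a limited form. The 40% does not match the row of Table 1 it is credited to, and 80% of 120 is 96. From the documented inputs about 34 offers are expected, and power is roughly 70–77% depending on the test and on how many patients are in fact offered a trial. Compared like for like, the loss is about 4–6 points. Importance is minor to moderate.

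Two stronger readings are tempting and should be resisted. One is that the 80% power was miscalculated; it reproduces at n = 40, and only the route to 40 is in question. The other is that 35% is the true offer rate, so that Aim 3 is established to be underpowered. Table 1's rows do not multiply through, they back-solve to about 43%, and the table is not specific to the thoracic clinic. At the back-solved rate the normal-approximation power would exceed 80%. The mismatch with the cited source is certain; the correct rate is not.

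**What to change.** In sections 2.3 and 2.7, write 96 patients with a trial available. Then choose one of two routes:

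- **(a)** Use Table 1's 35%, state about 34 expected offers, name the test, and restate power for 40% versus 60% as roughly 70–77% depending on the test and the realised number offered. Alternatively, give the rate detectable with 80% power at n = 34, about 61%.
- **(b)** Keep 40%, give its actual basis (rounding, an eligible-patient denominator, clinic mix, or an expected rise in offers) instead of crediting previous work, and show the 35% case as a sensitivity.

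Under either route, use one definition of availability in 2.3 and 2.7, and check it against the Aim 3 physician form, so that the offer rate and its denominator match.

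The cost is wording and stated figures only. Route (a) lowers the stated power; route (b) adds a sentence of justification and one sensitivity line. No patients or procedures are added.

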2.4 Study Flowchart

2.5 Study Procedures

Specific Aims in Detail

We have listed each specific aim with corresponding procedures and data analysis plan:

Specific Aim 1: *To determine whether TT delivery of educational clinical trial information can improve clinical trial knowledge overall and in within low literacy populations in particular.*

Hypothesis 1a: The interactive multimedia TT educational tool will results in significant gains in patients' pre-post assessments for each of the domains listed below.

Knowledge

Patients will self-administer pre- and post-tests on the TT. The Clinical Trial questionnaire was developed by Jacobsen and colleagues³ and contains the following items (see **Appendix 4**):

Attitudes toward clinical trials- 20 item likert measure of Positive attitudes toward clinical trials (eg, "being in a clinical trial benefits other patients") and negative attitudes (eg, "being in a clinical trial is likely to cause a patient harm. After reverse coding the negative items, responses to all items are combined into an average score (possible range, 1 to 5).

Knowledge about clinical trials-13 items have response options true, false, or don't know. The total score represents the number of items

answered correctly (possible range, 0 to 13).

Perceived ability (self-efficacy)- 9 item likert scale to measure ability to carry out actions involved in making an informed decision about clinical trial participation (eg, “I think I could get the information I need to decide whether to be in a clinical trial”). After reverse coding the negative items, responses to all items are combined into an average score (possible range, 1 to 5).

Willingness to participate in clinical trials will be measured using one likert scaled item: “If a cancer clinical trial were offered to you, would you agree to take part in it?” (“definitely yes” to “definitely no”).

Specific Aim 2: *To determine the feasibility and acceptability of TT in a busy urban academic medical center oncology clinic.*

Feasibility

The use of new information technologies has been recommended as a strategy for improving access to health information and for enhancing the quality of communication in healthcare delivery.⁹⁹ Our preliminary data show the number one reason that patients did not consent to a trial if offered was that they felt *overwhelmed by the information* (56%).

Hypothesis 2a: By providing the patient important information as to the options they may have in terms of their cancer treatment, directly prior to their talking with their physician and through use of an easy interactive tool, such as the proven TT in low-literacy populations, we will not interrupt or decrease the patient experience but enhance the physician-patient interaction, leading to increased participation in clinical trials.

This pilot study will provide to us the opportunity to understand the feasibility of using technology as a way to educate a cancer population about clinical trials within the healthcare environment of a busy, urban hospital setting. We will use this as an opportunity to understand how to integrate technology into clinic flow so that it is not disruptive but rather increases the efficacy of the physician-patient visit by educating patients as to clinical trials before seeing the physician. We estimate that the survey items will take 20-30 minutes to complete and that patients will spend **15-30 minutes with the TT**. Our experience is that 60 minutes is not an unreasonable burden, given the waiting time and other factors associated with a new visit. We will administer a simple evaluation questionnaire following the completion of the patient encounter with the TT, to measure their experience, including degree of difficulty.

Hypothesis 2b: The use of the TT will not effect clinic flow nor pose an additional burden to patient, physician or staff.

The researcher will also complete a simple questionnaire addressing the effect, if any, of introducing technology into the patient visit.

Data Analysis

We will administer a simple evaluation questionnaire to understand the patient's experience with the TT. We will adapt other questionnaires used in a previous TT study and will calculate descriptive summaries of the responses.

Specific Aim 3: *To evaluate the proportion of patients who sign consent to enroll in a cancer-specific treatment clinical trial when one is offered, compared to historical data.*

At the completion of the physician visit for that day, physicians will fill out a previously validated form asking the following questions:

- Is there a clinical trial here for this cancer and stage, regardless of the patient's other characteristics?
- Did you discuss a clinical trial with this patient?
- Did the patient specifically ask you about a clinical trial before you brought it up?
- Was the patient offered participation in a treatment-related clinical trial?
- If offered, did the patient sign consent?

Actual enrollment in a clinical trial (signed consent) will be confirmed using linkage to our clinical trial database, e-VELOS, which we used successfully in our previous study.

In our previous trial, 40% of patients offered a clinical trial enrolled in a trial. For our low literacy population, 30% enrolled when offered. We expect to be able to improve on these baseline values both by increasing patient understanding of the trial process and by improving their communication with their physician.

Specific Aim 4: To evaluate the associations between socio-demographics, health literacy, patient-reported outcomes (anxiety, depression, social support) and clinical trial enrollment, using the Behavioral Model for Vulnerable Populations.²⁵

Instruments

Tables 3 and 4 contain the instruments we will use:

TABLE 3: PROMIS INSTRUMENTS (www.nihpromis.org)

Construct	Social Support Measure Tools	Scoring for all PROMIS Psychometrics	Background Information/Psychometrics
PROMIS Companionship Scale	PROMIS V 2.0 short form-4 items. .	Reliability: The degree to which a measure is free of error. It can be estimated by the	PROMIS developed several instruments to measure the quality of social support, which refers to functional aspects of supportive relationships, i.e., interpersonal

		
internal consistency of the responses to the measure, or by correlating total scores on the measure from two time points when there has been no true change in what is being measured (for z-scores, reliability = 1 - SE²).
 
Standard Error (SE): The possible range of the actual final score based upon the scaled T-score. With a T-score of 52 and a SE of 2, the 95% confidence interval around the actual final score ranges from 48.1 to 55.9 (T-score + (1.96*SE) = 52+ 3.9 = 48.1 to 55.9). Alpha=0.96
 
Minimum number of items (4) must be answered in order to receive a score for emotional support CAT.
 
As additional items are administered, the potential for error is reduced and confidence in the respondent's score increases. CAT will continue until either the standard error drops below a specified level, or the participant has answered the maximum number of questions (12), whichever occurs first.
	
relationships that serve particular functions. This includes the interactive process by which emotional, instrumental or informational support is obtained from one's social network. It also includes companionship, feeling cared for and valued as a person, communication with others, and feelings of belonging and trust. Measures of social support generally seek information about a person's perception of the availability or adequacy of resources provided by others. The social support measures do not use a time frame (e.g. over the past seven days).
 
Assesses perceived availability of someone with whom to share enjoyable social activities such as visiting, talking, celebrations, etc.

PROMIS Emotional Support Scale	PROMIS v2.0 short form-8 items	Alpha=0.98	Assesses perceived feelings of being cared for and valued as a person; having confidant relationships.
PROMIS	PROMIS v2.0-	Alpha=0.95	Assesses perceived availability of

Informational Scale	8 item short form		helpful information or advice.
PROMIS Instrumental Support Scale	PROMIS v2.0-8 item short form	Alpha=0.96	Assesses perceived availability of assistance with material, cognitive or task performance.
PROMIS Anxiety Scale	8-item PROMIS Short Form V 1.0-Anxiety 8A	TEST INFORMATION 	Measures self-reported fear (fearfulness, panic), anxious misery (worry, dread), hyperarousal (tension, nervousness, restlessness), and somatic symptoms related to arousal (racing heart, dizziness). Anxiety is best differentiated by symptoms that reflect autonomic arousal and experience of threat. Only one behavioral avoidance item is included in the item bank; therefore, behavioral fear avoidance is not fully evaluated. The anxiety short form is generic rather than disease-specific. It assesses anxiety over the past seven days.
PROMIS Depression Scale	8-item PROMIS short form	TEST INFORMATION 	Assesses self-reported negative mood (sadness, guilt), views of self (self-criticism, worthlessness), and social cognition (loneliness, interpersonal alienation), as well as decreased positive affect and engagement (loss of interest, meaning, and purpose). Somatic symptoms (changes in appetite, sleeping patterns) are not included, which eliminates consideration of these items' confounding effects when assessing patients with comorbid physical conditions. The depression short form is generic rather than disease-specific. It assesses depression over the past seven days.

TABLE 4: ADDITIONAL INSTRUMENTS

Construct	Measure	Reference	Background Information/Psychometric
Demographics	Standard questionnaires used in our clinic.		Collecting employment, income, education, country of origin (including parents'), race, height, weight, marital status (i.e. married or cohabitating), length of marriage/relationship, specific cancer diagnosis and length of disease.
Medical Forms	1. Health Literacy single-item screener 2. Health	Wallace 2006 ¹⁰⁰ [name] et al.,	1. a single item previously validated by Wallace and colleagues in an urban university primary care clinic. • When compared to the Rapid Estimate of Adult Literacy in Medicine

	Literacy Assessment Using Talking Touchscreen Technology (Health LiTT).	2011 ¹⁰¹	
(REALM) instrument, the question, "How confident are you filling out medical forms by yourself?" had an Area Under the Receiver-Operator Curve (AUROC) of 0.82 (95% CI:0.77-0.86) for limited health literacy and 0.79 (95% CI:0.74-0.83) for limited or marginal health literacy.
 
 • Health LiTT is a novel, self-administered multimedia test that meets psychometric standards (reliability of 0.90 or higher) for measurement of individual respondents, especially in the low to middle range of health literacy. 
Health literacy has been previously shown to correlate with disparities in health outcome.

Comorbidities	Self-Administered Comorbidity Questionnaire (SCQ)	Katz et al., 2003	
 • Contains 12 medical conditions developed based on their frequency in general practice and their inclusion in published and commonly used comorbidity instruments. • Patients are asked if they have the condition, if they receive treatment for it and if the condition limits their activity. The highest possible score is 36, but in our survey will be 33 since we will eliminate the cancer comorbidity in that all patients have this in our cohort. • This survey has been shown to have excellent test-retest reliability (ICC of 0.81) and moderate to high concordance with the Charlson Index (kappa>= 0.46 for all conditions except lung disease). • In terms of predictive validity the instrument also has modest associations with health status one year after assessment of comorbidities as measured by correlations with the Physical Component Summary of the SF-36 (R2 0.22 of which 69% was explained by SCQ comorbidity score) and was superior to the Charlson Index in that regard.
Clinical Trial Knowledge Survey	Pre/Post Test Survey measuring change in knowledge, attitudes and beliefs and effect on behavior	Jacobsen et al., 2012 ³	Instrument measuring at baseline and follow-up: Attitudes towards clinical trials, knowledge about clinical trials, self-efficacy for clinical trial decision, receptivity to clinical trial information, willingness to participate in clinical trials.

Health Literacy- As in SA#2 above.

	
Psychosocial Measures-Participants will use the TT to complete short forms for anxiety, depression, and social support developed in the Patient-Reported Outcomes Measurement Information System (PROMIS) initiative (www.nihpromis.org). All PROMIS measures are based on T-scores, with a mean of 50 and a standard deviation of 10 in the reference population. Raw scores for this study will be calculated and then transformed to T-scores using PROMIS look-up tables (see http://www.assessmentcenter.net/Manuals.aspx).
 
In addition, the following tumor specific factors will be obtained-cancer type (NSCLC, SCLC), stage, and line of therapy for current stage as ascertained by physician survey but broken down as follows:
 
 • Never treated with chemo • Received first line treatment only • Received second-line treatment • Received three or greater lines of treatment. 
Data Analysis Categorical variables will be summarized as frequency counts and percentages and continuous variables will be summarized as medians and ranges. A logistic regression model will be set up with health literacy (as defined above) as the primary independent variable and enrollment in a clinical trial if one is offered as the primary dependent variable. The second model will control for race, income, cancer stage, line of treatment and co morbidity score.

2.6 Study Duration	Study duration will be 2 years.
2.7 Statistical Analysis and Sample Size Justification	
The principal investigator is supported by a Biostatistics Core Facility offered through the University Chicago's Comprehensive Cancer Center, which provides collaborative statistical support to investigators for the design, conduct, and analysis of clinical trials, observational and population-based studies, and basic science research projects.
 
Variables/Time Points of Interest These are described in detail under each specific aim listed in the Study Procedures section, above.
 
Statistical Methods These are described in detail under each specific aim listed in the Study Procedures section, above.
 
Sample Size: (Power described above under each Specific Aim.) For Specific Aims 1 and 2: Data Analysis

	
Three subscales on the pre- and post-questionnaire will assess attitudes towards clinical trials, knowledge about clinical trials and perceived ability. Change scores will be calculated and evaluated using a paired t-test. A sample size of 120 will have 80% power to detect an effect size as small as 0.258 using a paired t-test with a 0.050 two-sided significance level.
 
Based on our previous study, we estimate that 60% of these patients will have high health literacy (72) and the remaining 40% (48) will have low health literacy. We will evaluate differences in pre- and post-test changes by health literacy group. We will also estimate the correlation between change scores and the continuous measure of health literacy.
 
For Specific Aims 3 and 4: Based on the current clinical trial portfolio in the Thoracic oncology clinic (see Appendix 4), it is estimated that trials are available for 80% of the new patient population (including patient eligibility) (100 patients over 2 years) and of these, 40% will be offered participation (40). Our previous data suggested that when offered, 40% of these patients will sign consent. We hypothesize that our TT intervention will increase both the percentage of patients offered a trial (because of active participation from the patient in inquiring about trials) and in the percentage of patients who sign when offered. These impacts will be most profound in the low literacy group.
 
An effect size of 0.20 (H0: 0.4, HA:0.6) is a reasonable estimate for this pilot to be able to produce a clinically significant improvement in cancer clinical trial enrollment. A sample size of 40 (those offered enrollment) should give us 80% power to detect a 20% difference in trial enrollment from our baseline hypothesized value of 40% at a one-sided alpha level of 0.05.

2.8 Specific Drug Supply Requirements
	
NA

2.9 Adverse Experience Reporting
	
NA

2.10 Itemized Study Budget
	
A preliminary study budget must be provided with the initial proposal submitted to give guidance to the MISP Review Committee as to the expected study costs. A refined itemized budget detailing the costs associated with the study should be provided with the final protocol or included in the study agreement as Exhibit B.

References

1. Comis RL, [name] JD, Aldige CR, et al: Public attitudes toward participation in cancer clinical trials. *J Clin Oncol* 21:830-5, 2003
